4.4 Medical History and Concurrent Medical Conditions

Medical history was not re-assessed at the start of the open-label extension period, but will be reported for the OL-SAF population.

Medical history and concurrent medical conditions are to be summarized for the OL-SAF population.

Medical history will be collected on the “Medical History” eCRF page. Medical history will be coded using MedDRA and summarised by MedDRA System Organ Class (SOC) and Preferred Term (PT), and by treatment sequence and all sequences pooled. Text “Not Coded” will be displayed in case terms are not coded.

The data will also be listed for OL-SAF population, including the verbatim Investigator description of the relevant medical condition, the coded terms (SOC, PT), start date, end date, whether or not the condition is ongoing and treated.

4.5 Prior and Concomitant Medications and Procedures

4.5.1 Prior and Concomitant Medications

Prior and concomitant medications are to be summarized for OL-SAF population.

Prior and concomitant medications will be collected on the “Prior and Concomitant Medications” eCRF page. All medications will be coded using the World Health Organization Drug Dictionary.

A prior medication is defined as any medication taken any time with an end date before the date of the first administration of investigational product in the double-blind period. Note that these are identical to the prior medications for the double-blind analyses, but subset to the OL-SAF population.

A concomitant medication during the open-label extension period is defined as any medication/therapy taken from the first dose administration of investigational product in the open-label extension period through the end of treatment or early termination visit of the open-label extension period.

Counts and percentages of subjects use for each concomitant medication during open-label extension period will be tabulated by ATC Level 2 and ATC Level 4 and by treatment group.

In addition, prior and concomitant antipruritic medications during the open-label extension period will be summarized separately by ingredient and by treatment sequence and all sequences pooled. These medications will be selected using “reason for treatment” = “Disease under study” collected on the “Prior and Concomitant Procedures” eCRF page; however, a medical review will be performed to ensure correctness.

Any prior medication and any concomitant medication collected on the eCRF will be presented in a by-subject listing.

4.5.2 Prior and Concomitant Procedures

Prior and concomitant procedures will be collected on the “Prior and Concomitant Procedures” eCRF page. All the prior and concomitant procedures collected on the eCRF will be presented in a by-subject listing.

4.6 Study Drug Exposure and Compliance

Study drug exposure and compliance are to be summarized and listed for OL-SAF population.

Study drug exposure data during open-label extension period will be collected on the “Study Drug Administration-Open label” eCRF page and the dialysis data will be collected on the “Dialysis-Open label” and “Dialysis Type Adjustment” eCRF page. Note that dialyses after last dose may be collected on the “Dialysis-Open Label” eCRF page. Only dialysis from open-label extension period Day 1 until the last dialysis prior to EoT or ET visit will be included as dialysis during the open-label extension period.

For this study, the duration of open-label treatment for each individual subject is expected to be 14 weeks, for a total of approximately 42 doses of study drug administered immediately following each dialysis session. The last day of the open-label treatment period will be defined as the day of the last injection of investigational product + 2.5 days, as there would be 2-3 days from the last dose to the next dialysis.

Study drug administration and treatment compliance during the open-label extension period is to be summarised by treatment sequence and all sequences pooled by the following parameters:

- Duration of open-label treatment (days): calculated as (date of the last dose + 2.5) – (date of first dose) + 1
- Total number of doses actually received as continuous and categorical variables (1-3, 4-6, 7-9, etc.)
- Number of missed doses as continuous and categorical variables (1-3, 4-6, 7-9, etc.)
- Average dose per administration (mcg/kg): calculated as actual dose (ml) * 50 mcg/ml (strength) / prescription dry body weight (kg). Noted the prescription dry body weight is to be captured on Day1 and at Week 12 during the open-label extension period. The most recent value is to be used for the calculation.
- Average dose per administration (mcg): calculated as actual dose (ml) * 50 mcg/ml (strength)
- Number of subjects with extra doses: (1, 2, 3, >=4 doses)
- Compliance (%): calculated as actual doses/planned doses (defined below)

Dialysis performed during the open-label extension period is to be summarized by treatment sequence and all sequences pooled by the following parameters:

- Total number of dialysis visits logged as a continuous and categorical variable (1-3, 4-6, 7-9, etc.)
- Number of missed dialysis visits as a continuous and categorical variable (1-3, 4-6, 7-9, etc.)
- Number of subjects with extra dialysis: (1, 2, 3, >= 4 doses)

- Dialysis Compliance (%): calculated as sum of the actual dialysis visits/sum of the planned dialysis visits (defined below)

Per protocol, if a subject receives additional dialysis during a given week for any reason, an additional dose of investigational product will be administered following dialysis. A maximum of 4 doses per week is allowed. No additional doses will be given for subjects receiving an additional unscheduled ultrafiltration treatment.

The number of planned doses/dialyses will be derived as follows:

- Step 1: For subjects who completed treatment with a “No” noted for the question “Did the subject discontinue the treatment prematurely?”, number 42 (14 weeks and 3 times for each week) is assigned. For subjects who did not complete the open-label extension period, the following steps will be applied.
- Step 2: Keep all the doses/dialyses data during open-label extension period for each subject.
- Step 3: Check how far they were into the time point of the last dose/dialysis during the open-label extension period. For example, if the time point is “Week 8-Scheduled First”, then the planned dose/dialysis is calculated as 22 times (7 weeks * 3 times/week + 1 time in week 8). If the time point is “Week 9-Scheduled Third”, then the planned dose/dialysis is calculated as 27 times (8 weeks * 3 times/week + 3 times in week 9).

Missed doses/dialyses will be determined as follows:

- Step 1: Keep all the doses/dialyses data during open-label extension period for each subject.
- Step 2: Determine the last time point during the open-label extension period for each subject.
- Step 3: Create a dummy dataset with each time point for each subject. For subject who completed treatment with a “No” noted for the question “Did the subject discontinue the treatment prematurely?”, number 42 (14 weeks and 3 times for each week) is assigned. For subjects who did not complete the open-label extension period, the following steps will be applied.
- Step 4: Merge the dummy dataset with the dataset including subjects’ actual doses/dialyses by each subject and each time point.
- Step 5: Count the number of time points with no actual doses/dialyses for each subject.

Extra doses/dialyses will be determined as follows:

- Step 1: Keep all the doses/dialyses data during open-label extension period for each subject.
- Step 2: Extra doses/dialyses are collected as records with time point = “Unscheduled Visit”.
- Step 3: In case of the unexpected circumstance that are multiple records for a specific scheduled time point, only one time would be considered as the planned dose/dialysis, the other doses/dialyses would be considered as “extra”.
- Step 4: Sum the “extra” times from step 2 and step 3.

All the dialysis data and dialysis type adjustment after the first dose date in the open-label extension as well as dialysis type adjustment data will be presented in listings.

All the study drug administration, study drug exposure, dialysis, and compliance data of the open-label extension period will be presented in listings.

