8.1 Allowed Adaptations in Case of Extraordinary Events, e.g., COVID-19

The guidance below is intended for subjects who have been successfully enrolled into the study and who are unable to attend in person clinic visits due to COVID-19 restrictions. Every reasonable effort should be made to ensure that the subject continues on the study per-protocol. Study visits which coincide with dialysis days should be conducted on-site. In the event that a subject cannot come to the clinic after baseline visit due to self-quarantine, local restrictions, or illness, a visit at another local hospital may be considered.

If the subject misses, or is expected to miss, 2 consecutive clinic visits due to COVID-19, the Investigator must contact the Medical Monitor to discuss discontinuation of the subject from the study. In either scenario, the subject should return to the clinic for assessment at their earliest convenience. If it is determined that the subject must be discontinued, the reason for termination should be documented as ‘related to COVID-19’ under Reason for Termination: Other in the eCRF.

Extraordinary events may call for specific measures to maintain subject safety and guarantee conduct of clinical investigations according to established general and specific guidelines and regulations to meet agreed regulatory, quality, and scientific expectations.

For this, the following adaptations are considered for specific situations:

- Site visits are not possible within the defined time window, possibly leading to delayed visit:
 - On-site monitoring: accept delayed on-site monitoring, conduct remote monitoring.
 - On-site auditing: accept delayed on-site auditing, conduct remote auditing.
 - AE/SAE/special situation reporting: frequent phone call visits.
- Site visits are not possible within the defined time window, possibly leading to no visit:
 - Vital signs: consultation by local physician, follow-up clinical assessment via phone remote visits at subject’s home (e.g., home nursing).
 - On-site monitoring: accept delayed on-site monitoring, conduct remote monitoring.
 - On-site auditing: accept delayed on-site auditing, conduct remote auditing.

- AE/SAE/special situation reporting: frequent phone call visits.

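### For open-label early stoppers, planned doses end at the last dose given, so scheduled doses missed between that dose and stopping do not lower compliance, and the missed-dose count has no defined end

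*SAP*

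**What the plan says.** SAP 4.6 defines open-label compliance as actual doses divided by planned doses. For a subject who completed treatment, "number 42 (14 weeks and 3 times for each week) is assigned". For a subject who did not, the planned number is read off the last recorded position: "Step 3: Check how far they were into the time point of the last dose/dialysis during the open-label extension period". The two worked examples give 22 planned doses for a last time point at the first session of Week 8, and 27 for the third session of Week 9.

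Missed doses have their own steps. The programmer is told to "Determine the last time point during the open-label extension period for each subject", to build a grid of time points, to merge it with the actual records, and then to "Count the number of time points with no actual doses/dialyses for each subject". For completers the grid has 42 slots. For non-completers the text only refers forward to the following steps and does not say where the grid stops.

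Dialyses have an explicit end: "Only dialysis from open-label extension period Day 1 until the last dialysis prior to EoT or ET visit will be included". The same section notes that dialyses after the last dose may be on file.

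**The concern.** The denominator for an early stopper is fixed by the last dose received, which is part of what compliance is meant to measure. Any scheduled dose withheld or missed after that dose, but before treatment is stopped, lies outside the denominator by construction. The error can only run one way, towards higher compliance, and only in subjects who stop early. Completers are handled by a different rule: their denominator stays at 42, so doses missed at the end do count against them.

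The situation can be foreseen from the SAP itself. It expects dialyses after the last dose, and SAP 4.8.1 separates adverse events that led to interruption of the drug from those that led to withdrawal, so an interruption that becomes a withdrawal is possible. The open-label exposure table is background for reading the extension's safety data, so its compliance line should mean the same thing for stoppers and completers.

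**Working it through.** **Inputs (SAP 4.6).** Three scheduled doses a week for 14 weeks; planned doses for early stoppers end at the last dose; compliance = actual / planned.

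**1. Reproduce the SAP's figures.** Planned = 3 × (week − 1) + session number.
- Week 8, first session: 3 × 7 + 1 = 22.
- Week 9, third session: 3 × 8 + 3 = 27.
- Week 14, third session: 3 × 13 + 3 = 42.

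All three agree with the SAP.

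**2. Vary the doses missed after the last dose.** Take the last dose at Week 8, first session, with no earlier gaps and no extra doses. Let t be the number of scheduled doses missed between that dose and the stopping of treatment. The documents do not give t, so its values here are assumptions. The SAP rule gives 22/22 for every t; counting to the stop gives 22/(22 + t).

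| t | SAP rule | Counted to the stop |
|---|---|---|
| 0 | 100% | 22/22 = 100% |
| 1 | 100% | 22/23 = 95.7% |
| 2 | 100% | 22/24 = 91.7% |
| 3 | 100% | 22/25 = 88.0% |
| 5 | 100% | 22/27 = 81.5% |
| 6 | 100% | 22/28 = 78.6% |

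**3. Compare with a completer.** A completer who misses the last 5 doses scores 37/42 = 88.1%. The early stopper who misses 5 doses just before stopping scores 100% under the rule.

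**4. See what the rule does capture.** With the same last dose, 2 gaps before it give 20/22 = 90.9%, and 4 gaps give 18/22 = 81.8%. One extra dose with no gaps gives 23/22 = 104.5%, because nothing in the formula removes extra doses from the numerator.

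**5. Test the missed-dose count at t = 2.** When there are no extra doses, planned should equal actual plus missed.
- Grid ends at the last dose: planned 22, actual 22, missed 0. The figures agree with each other, but the 2 doses have vanished.
- Grid ends at the last dialysis before ET, with both sessions attended: planned 22, actual 22, missed 2. Then 22 + 2 = 24, not 22.
- One common cut-off at the stop: planned 24, actual 22, missed 2. Then 22 + 2 = 24.

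**6. Set dose and dialysis compliance side by side.** If both undosed sessions were attended, dialysis compliance is 24/24 = 100% and dose compliance is 22/22 = 100%. Neither percentage shows that two attended dialyses had no dose.

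**The case against.** The schedule limits the gap. In SAP Table 2 the end-of-treatment visit, which shares a column with early termination, is the first dialysis visit after the last dose. SAP 4.6 also ends the treatment period 2.5 days after the last injection. Where ET falls on the first scheduled dialysis after the last dose, t is 0 and the rule does no harm. This stands, and it confines the point to later ET visits.

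The information is also not lost. Doses received and dialyses logged are both summarised, Listing 16.2.5.2 puts exposure, dialysis and compliance together by subject, and adverse events leading to interruption or discontinuation are tabulated. That is true, but a reader of the compliance line would have to rebuild the correct figure from listings.

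Three stronger readings are tempting, and the documents do not support them.
- A reader might infer that every early stopper shows 100%. Step 4 shows otherwise: earlier gaps lower the figure and extra doses can raise it above 100%.
- A reader might infer that doses missed after the last dose are never counted as missed. The missed-dose steps speak of a last time point, not a last dose, so they may be counted. Whether they are may also depend on how scheduled but undosed sessions are recorded in the eCRF, which the documents do not show.
- A reader might infer that a run of missed doses is the usual way out of the study. Protocol 8.1 is the nearest support, and it is limited to COVID-19: "If the subject misses, or is expected to miss, 2 consecutive clinic visits due to COVID-19, the Investigator must contact the Medical Monitor". It leads to a discussion of discontinuation and says nothing about how subjects generally leave.

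**Conclusion.** The point holds in a limited form. For early stoppers, SAP 4.6 leaves scheduled doses missed between the last dose and the stop out of planned doses, by a rule that differs from the one for completers. The missed-dose count then either omits the same doses or contradicts planned doses, depending on how the undefined last time point is read.

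For one subject with the last dose at slot 22 and no earlier gaps or extra doses, compliance is overstated by 100 − 91.7 = 8.3 points if 2 doses were missed before stopping, and by 100 − 78.6 = 21.4 points if 6 were. The effect on the group mean cannot be derived. It needs the share of subjects who stop early, the share of those with ET later than the first scheduled dialysis after the last dose, and the number of doses missed. The documents give none of these for the extension; the 10% dropout figure in SAP 2.4 belongs to the double-blind sample size.

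Only the descriptive exposure and compliance summary is affected. The OL-SAF requires one open-label dose, so no analysis population, efficacy model or adverse event table depends on compliance. This is a minor point that is cheap to correct.

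**What to change.** In SAP 4.6, give early stoppers one common cut-off for planned and missed doses: the last scheduled time point before the EoT/ET visit, or before the documented date of the decision to withdraw the drug if that is earlier. Count every scheduled slot up to that point whether or not dialysis took place, cap the count at 42, and treat a slot with no dose as missed.

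Two details matter. Counting slots rather than recorded dialyses is needed because a session at which dialysis itself was missed leaves no dialysis record. Using the withdrawal decision when it is earlier avoids counting sessions at which no dose was intended any more. SAP 4.1.4 already takes a treatment stop date from the Treatment Termination page. The SAP should say whether that date is the decision or the last dose, because a date equal to the last dose would bring the problem back.

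The cost is a sentence or two in the SAP and a small change to the derivation program. Reported compliance will become slightly less favourable.

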4.7 Efficacy Analyses

Itch-related QoL including 5-D itch scale and Skindex-10 scale will be collected for the evaluation of the efficacy in the open-label extension period.

4.7.1 5-D Itch Scale

The 5-D Itch Scale was developed as a brief, multidimensional questionnaire designed to be useful as an outcome measure in clinical trials. The 5 dimensions of itch being assessed are degree, duration, direction, disability, and distribution (see protocol Appendix 4).

The duration, degree, and direction domains each include 1 item, while the disability domain has 4 items. All items of the first 4 domains were measured on a 5-point Likert scale. The distribution domain included 16 potential locations of itch, including 15 body part items and 1 point of contact with clothing or bandages.

Single-item domain scores (duration, degree, and direction) are equal to the value indicated below the response choice (range 1-5). The disability domain includes 4 items that assess the impact of itching on daily activities: sleep, leisure/social activities, housework/errands, and work/school. The score for the disability domain is calculated by taking the highest score on any of the 4 items. For the distribution domain, the number of affected body parts is tallied (potential sum 0-16), and the sum is sorted into 5 scoring bins: sum of 0-2 = score of 1, sum of 3-5 = score of 2, sum of 6-10 = score of 3, sum of 11-13 = score of 4, and sum of 14-16 = score of 5.

The scores of each of the 5 domains are calculated separately and then summed together to obtain a total 5-D score. 5-D scores can potentially range between 5 (no pruritus) and 25 (most severe pruritus).

Total 5-D Itch score = duration score (single item) + degree score (single item) + duration score (single item) + maximum (4 disability items) + category score based on sum of affected body parts.

The scoring manual does not give specific direction regarding scoring when some questions are missing; therefore, each domain and the total score will be set to missing when any of their individual components are missing, with the exception of the disability domain. The maximum of any items present for disability will be used for that domain.

Analyses

The 5-D itch scale scores will be analysed using an MMRM model. The model will contain treatment sequence, week, and treatment-by-week interaction as fixed effects, and baseline score and the randomization stratification variables as covariates.

Two independent analyses will be presented, one using baseline from the open-label extension period and one using baseline from the double-blind period. The first analysis will include all visits in the open-label extension period, with the first baseline definition defined in section [4.1.2](#). The second analysis will include all visits from both the double-blind and open-label periods, with the second baseline definition defined in section [4.1.2](#).

Separate models will be used for the 2 different changes from baselines described above. An unstructured covariance matrix will be used to model the within-subject errors. Should the model fail to converge, a compound symmetric covariance matrix will be used instead. The Kenward-Roger2 approximation will be used to estimate the denominator degrees of freedom. Missing scores will not be imputed. Assuming that the data are missing at random (MAR), the estimates calculated from the MMRM described above are unbiased.

Standard descriptive statistics will be reported for each time point on the values and changes from baseline along with the least squares (LS) means, standard errors, 95% confidence intervals (CIs), and differences from baseline within each treatment sequence reported with LS means, standard errors, and 95% CIs. Plots will also be created.

The above analyses for the 5-D itch scale total score will be repeated for each of its domain scores.

As a separate analysis, the number and percentage of subjects that have a 5 point or greater improvement of the 5-D itch scale total score will be reported by visit and treatment sequence. Additionally, the percentage and 95% CIs estimated using a logistic regression model, containing terms for treatment sequence, baseline total 5-D score, use of anti-itch medication during the week prior to randomization, and presence of specific medical conditions, will be presented. This analysis will be performed using the baseline from the double-blind period.

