9.7.2 Skindex-10 Scale

Developed specifically for uraemic pruritus, the Skindex-10 scale ([Appendix 3](#)) is an instrument for measurement of QoL that correlates with itch intensity [\[17\]](#). Subjects are asked to mark 1 of 7 boxes numbered from 0 (labelled with the anchor phrase “never bothered”) to 6 (labelled as “always bothered”) for each of the 10 questions describing how often they have been bothered by their itch and its impact over the past week. The total score is the sum of the numeric value of each answered question. The total score is subdivided into 3 domain scores, which are sums of the scores of the following questions: disease domain (questions 1 to 3), mood/emotional distress domain (questions 4 to 6), and social functioning domain (questions 7 to 10).

9.7.3 5-D Itch Scale

The 5-D itch scale was developed as a brief, multidimensional questionnaire designed to be useful as an outcome measure in clinical studies. The 5 dimensions of itch assessed are degree, duration, direction, disability, and distribution ([Appendix 4](#)). Subjects are asked to mark boxes that best describe the impact of their itch over the past 2 weeks. The scale has been validated in patients with chronic pruritus, including HD patients and has been shown to be sensitive to changes in pruritus over time [\[19\]](#).

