Appendix 4 5-D Itch Scale

1.	DURATION:	During the last 2 weeks, how many hours a day have you been itching?						
		Less than 6 hrs/day	6-12 hrs/day	12-18 hrs/day	18-23 hrs/day	All day		
								
2.	DEGREE:	Please rate the intensity of your itching over the past 2 weeks						
		Not present	Mild	Moderate	Severe	Unbearable		
								
3.	DIRECTION:	Over the past 2 weeks has your itching gotten better or worse compared to the previous month?						
		Completely resolved	Much better, but still present	Little bit better, but still present	Unchanged	Getting Worse		
								
4.	DISABILITY:	Rate the impact of your itching on the following activities over the last 2 weeks						
		Sleep	Never affects sleep	Occasionally delays falling asleep	Frequently delays falling asleep	Delays falling asleep and occasionally wakes me up at night	Delays falling asleep and frequently wakes me up at night	
								
		Leisure/Social	N/A	Never affects this activity	Rarely affects this activity	Occasionally affects this activity	Frequently affects this activity	Always affects this activity
								
		Housework/ Errands						
								
Work/School								

5. DISTRIBUTION:	Mark whether itching has been present in the following parts of your body over the last 2 weeks. If a body part is not listed, choose the one that is closest anatomically.			
	Head/Scalp		Soles	

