2.6.2 Efficacy Endpoint for Open-label Extension Period

- Change from baseline in itch-related QoL at each time point of the open-label extension phase, as assessed by the 5-D itch scale total score.
- Change from baseline in itch-related QoL at each time point of the open-label extension phase, as assessed by the Skindex-10 scale total score.

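### The SAP's equation for the 5-D itch total adds duration twice and omits direction, so the open-label 5-D endpoint and its 5-point responder analysis are mis-scored if programmed as written

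*SAP*

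**What the plan says.** The SAP for the open-label extension names the 5-D total in one of its two efficacy endpoints (section 2.6.2): "Change from baseline in itch-related QoL at each time point of the open-label extension phase, as assessed by the 5-D itch scale total score".

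Section 4.7.1 describes the score in two ways.

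- **In prose.** It lists the domains: "The 5 dimensions of itch being assessed are degree, duration, direction, disability, and distribution". It then scores the single items: "Single-item domain scores (duration, degree, and direction) are equal to the value indicated below the response choice (range 1-5"). Disability takes the worst of its four items, and distribution is a count of body sites binned to 1–5. The rule for the total is: "The scores of each of the 5 domains are calculated separately and then summed together to obtain a total 5-D score". The stated range of the total is 5 to 25.
- **As an equation.** "Total 5-D Itch score = duration score (single item) + degree score (single item) + duration score (single item) + maximum (4 disability items"), and then a last term, "category score based on sum of affected body parts".

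Protocol section 9.7.3 lists the same five dimensions, direction included: "The 5 dimensions of itch assessed are degree, duration, direction, disability, and distribution". Protocol Appendix 4 collects direction as question 3: "Over the past 2 weeks has your itching gotten better or worse compared to the previous month". SAP section 1.2, which lists departures from the protocol, mentions added responder analyses but no change to 5-D scoring.

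**The concern.** The equation contradicts the prose directly above it: duration carries double weight and direction carries none. Direction is the item that asks whether itch has improved or worsened, so the item most directly concerned with change drops out of a change-from-baseline endpoint.

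A good deal depends on this total. It is the response in two MMRM analyses, one from the open-label baseline and one from the double-blind baseline across both periods. Its baseline value is a covariate in those models and in the logistic model. It defines the responder analysis (improvement of 5 points or more) and the related tables and figures, including Tables 14.2.1.1, 14.2.1.2 and 14.2.2.1.

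**Working it through.** **Inputs.** Each of the five domains is scored 1–5 (SAP 4.7.1). The stated range of the total is 5–25 (same section). A responder improves by at least 5 points (SAP 4.7.1, Analyses). Item scores fall as itch improves.

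**Step 1: the stated range under the prose rule.** P = duration + degree + direction + disability + distribution. The minimum is 5 × 1 = 5 and the maximum 5 × 5 = 25, which reproduces the SAP's range.

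**Step 2: the range under the equation.** F = 2 × duration + degree + disability + distribution. The minimum is 2 + 1 + 1 + 1 = 5 and the maximum 10 + 5 + 5 + 5 = 25. The range is identical, so a range check cannot tell the two apart.

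**Step 3: error in a single total.** F − P = duration − direction. The extremes are 1 − 5 = −4 and 5 − 1 = +4. The error is zero only when the two items are equal, which is 5 of 25 possible pairs; the other 20 of 25 (80%) give a wrong total. This counts score combinations and is not an expected frequency in patients.

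**Step 4: error in a change from baseline.** ΔF − ΔP = Δduration − Δdirection. Each item can change by −4 to +4, so the error runs from −8 to +8. It vanishes when both items move by the same amount.

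**Step 5: effect on responder status.** These are hypothetical subjects, with scores in the order duration, degree, direction, disability, distribution.

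| Baseline → follow-up | Prose rule | Equation |
|---|---|---|
| 2,4,4,4,3 → 1,3,2,3,3 | 17 → 12, change −5, responder | 15 → 11, change −4, non-responder |
| 2,4,4,4,3 → 2,3,2,3,2 | 17 → 12, change −5, responder | 15 → 12, change −3, non-responder |
| 4,4,4,4,3 → 2,3,4,3,3 | 19 → 15, change −4, non-responder | 19 → 13, change −6, responder |

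Misclassification can go either way.

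**Step 6: an illustration of scale, on assumed data.** The documents give no 5-D item data, so these inputs are assumptions. The latent baseline means are 2.5, 3.5, 3.9, 3.5 and 3 in the same order. The latent mean changes are −1.0 for degree, −1.0 for disability and −0.6 for distribution, with duration and direction varied. Variance is 0.9 and pairwise correlation 0.5. Scores are rounded and held within 1–5.

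| Latent mean change: duration, direction | Mean change, prose / equation | Responders, prose / equation | Subjects reclassified |
|---|---|---|---|
| −0.5, −1.5 | −4.11 / −3.05 | 46.0% / 33.8% | 13.3% |
| −0.8, −1.2 | −4.07 / −3.49 | 45.5% / 38.5% | 10.2% |
| −1.0, −1.0 | −4.02 / −3.75 | 44.6% / 41.4% | 9.1% |
| −1.2, −0.8 | −3.97 / −4.00 | 43.7% / 44.0% | 9.2% |

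Under these assumptions the mean shifts by between about 0 and 1.1 points, and roughly 9% to 13% of subjects change class. Even where the mean barely moves (last row), about 9% are reclassified.

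**Step 7: two side effects of the literal equation.** First, SAP 4.7.1 sets the total to missing when any component is missing, with an exception for disability items. The equation never calls on direction, so it would return a total when direction is unanswered. Second, Tables 14.2.1.1 and 14.2.1.2 show the total beside each domain, and a subject's five domain scores would not add up to the reported total whenever duration and direction differ.

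**The case against.** The best counter-argument is that this is a slip of the pen with the right rule beside it. The prose names direction, scores it and says the five domains are summed. The domain analyses require direction to be derived anyway, so a programmer who adds up the derived domains gets the correct total. The affected results are also modest in standing. The extension is uncontrolled, this SAP reports 5-D estimates within treatment sequence without a specified hypothesis test, and the 5-point responder analysis is an SAP addition.

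Part of this stands. Results are wrong only if the program follows the equation, and the documents do not show which text was coded. The practical size is unknown, and the item scores used above are invented. The error touches no confirmatory result.

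It does not clear the equation. Of the two statements, the equation is the one in a form ready to be coded. The protocol gives no equation for the total that could settle the conflict, and SAP section 1 gives the SAP precedence over the protocol. Section 1.2 gives no sign of a deliberate change, and the most obvious automatic check would pass the wrong score.

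**Conclusion.** The equation is wrong as written and must be corrected. Its error is exactly duration minus direction: −4 to +4 points per total and −8 to +8 points on change, against a 5-point threshold, with responder status able to move in either direction. These bounds rest only on the SAP's own 1–5 scoring. The typical effect cannot be determined from the documents, and the simulated figures show only what is plausible under stated assumptions.

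The consequence is confined to the 5-D total, its baseline covariate and the 5-point responder analysis in this SAP. The overall-study versions of these analyses also draw on double-blind visits. The primary WI-NRS endpoint, Skindex-10, the individual 5-D domain analyses and the safety analyses are untouched. The double-blind SAP was not available, so nothing is concluded about it.

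**What to change.** In SAP section 4.7.1, change the second duration term of the equation to direction, so that it reads duration + degree + direction + worst disability item + distribution bin. Then confirm which version the derivation program uses. For every record, compare the derived total with the sum of the five domain scores, and confirm that a missing direction answer makes the total missing. If any output was produced from the literal equation, rerun the 5-D total tables and figures and the responder analysis. As a precaution, check whether the same equation appears in the double-blind SAP, since the overall-study analyses here use visits from that period.

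The cost is one word in the SAP and one programming check, plus reruns if the check fails. No new data are needed, because direction is already collected and scored.
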